# Acceptability will be determined by responses to the following questions (evaluated at FU):

- 1. If you ever were to have another termination of pregnancy, would you opt for the same method of counselling? Yes/No/Doesn't matter
- 2. If you ever have another termination of pregnancy, would you prefer the counselling at the healthcare facility or to be responsible for your own counselling via telemedicine? 1 or 2
- 3. If you've previously had an abortion, how would you compare your experience this time with your previous treatment? Much worse, Worse, Similar, Better, Much better
- Acceptability of counselling procedure

Women will be asked to rate acceptability of counselling from 1 to 4

- 1, completely acceptable;
- 2, fairly acceptable;
- 3, fairly unacceptable;
- 4, completely unacceptable.

# 5. Eligibility criteria

*Inclusion criteria:* Women 18 years old and above, requesting termination of pregnancy by means of mifepristone followed by home administration of misoprostol at < /=63 days of gestation, with no contraindication to medical abortion and self administration of misoprostol at home, and who have given their informed consent will be eligible for study recruitment.

Exclusion criteria: Women who do not wish to participate, women who do not want home administration of misoprostol, women who are unable to communicate in Swedish, or English, and women with symptoms and signs of ectopic pregnancy. Minors (i.e. women < 18 years of age) will not be enrolled in the study. Women seeking termination of pregnancy with no visible intrauterine pregnancy.

# 6. Trial process and data collection

The study protocol is designed according to the recommendations in the CONSORT statement for non-inferiority trials. The study is performed at the gynaecological outpatient department (SESAM) at the Karolinska university hospital, (and additional sites according to the amendment)

The study flow is planned as follows:

# **Enrolment**

All women with a pregnancy up to 63 days gestation requesting termination of pregnancy by medical methods and opting for home administration of misoprostol will be invited to be included in the study at the initial telephone consultation. The women

will receive detailed information regarding the study, and give oral consent to participation.

Consent will also be obtained online and at the visit to the clinic prior to ultrasound examination and intake of mifepristone.

### Allocation and treatment

Eligible women with a pregnancy up to 63 days gestation who elect to participate in the study will be randomized into either:

Group 1 telemedicine counselling, or

Group 2 standard face-to-face counselling

Study participants will be administered mifepristone and provided with misoprostol and pain medication at the time of the ultrasound scan (Group 1) or at routine counselling (Group 2).

Randomization will take place after women have given their oral informed consent at the telephone consultation. Randomization will be by opening of opaque sealed envelopes by a nurse midwife. The envelopes will be prepared by a study coordinator at the WHO center of Karolinska University Hospital who will have no further contact with women. Designated nurse/midwives and doctors will be responsible for recruiting study participants at the telephone booking and research midwives/doctors for ultrasound scans in the outpatient clinic (group1) while standard care (Group 2) will be provided according to routine.

### Website

Women randomised to Group 1 (telemedicine counselling) will receive the address to a designated website. The content of counselling will include eligibility criteria, information regarding the treatment course, expected effects, side effects and signs and symptoms of complications. All women will also receive contact information to a help desk and information on when and where to contact in case of need.

Women randomised to study Group 1 will receive an appointment for an ultrasound scan, mifepristone treatment, chlamydia test and pick up of study medication. A nurse midwife/doctor will be responsible for the ultrasound scan to confirm intrauterine pregnancy and gestational length. Following the ultrasound scan mifepristone will be swallowed in the clinic according to the Swedish law. No further abortion counselling will be provided at this visit. However contraceptive counselling and prescription is provided as needed.

### Follow-up

A follow-up telephone call or web-based questionnaire to assess outcomes of treatment will be done by a nurse midwife or doctor approximately three weeks following the treatment (both groups). Women in the clinical routine group could choose to come back to the clinic for follow up. Appointments for postabortion contraception will be done as required.

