Our studies have shown that telemedicine and provision of medical abortion through wow is safe, acceptable and with outcomes similar to medical abortion provided traditionally following face-to-face counselling (Gomperts et al., 2008, 2011, 2014, Grossman et al., 2011). Furthermore, recently home self-assessment of the abortion outcome through a low sensitivity U-hCG test and a checklist was shown to be highly accepted to women (Sunde Oppegaard et al., 2015, lyengar et al., 2015). In our study on home use of misoprostol a vast majority of women (99%) stated that they would also have preferred to administer mifepristone at home. However, according to the Swedish law medical abortion has to be performed in an approved health facility. The abortion is legally defined as being performed when mifepristone is swallowed. Thus, home use of misoprostol is allowed according to the law although the expulsion of the products of conception usually occurs following the administration of misoprostol.

To evaluate whether counselling through telemedicine is non-inferior to face-to face counselling a RCT will be conducted including women who chose medical abortion up to 63 days of gestation with home administration of misoprostol and self assessment of the outcome. The results of this study could be of major importance to increase access to safe abortion services. Telemedcine counselling has never been evaluated in a RCT.

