# Group 1: intervention

Telemedicine counselling. Ultrasound and mifepristone at outpatient clinic, to be continued with home administration of misoprostol at 24-48 hours later and self assessment of outcome 2-3 weeks after mifepristone.

Group 2: Control

Routine appointment with the abortion clinic with face-to-face counselling, ultrasound dating and mifepristone at outpatient clinic, to be continued with home administration of misoprostol at 24-48 hours later and self assessment of outcome 2-3 weeks after mifepristone.

Both groups: Self assessment of outcome will be done by the hCG CheckTop test (Exelgyn/Veda Lab (Alençon, France) (Sunde Oppegaard et al., 2015 as used in clinical routine. A Follow-up online questionnaire to evaluate success of procedure and satisfaction with treatment, contraception uptake etc will be done approximately 2-3 weeks after mifepristone to evaluate success of procedure. An email or telephone reminder will be sent if the online contact is unsuccessful. The patient (electronic) records will be reviewed after 30 days in order to control for possible extra visits related to abortion-related complications.

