### 4. Outcome measures

# Primary outcome

Efficacy of medical abortion defined as complete abortion without ongoing intrauterine pregnancy or surgical intervention for incomplete abortion within 30 days of the abortion treatment. The outcome will be determined based on the home low sensitivity uhCG and patient records (surgical intervention).

Secondary outcomes will include safety (AE/SAE), any additional medical treatment of incomplete abortion, bleeding days and estimated amount, infection, surgical treatment for other indications than ongoing pregnancy or incomplete abortion, unscheduled contacts and visits, acceptability with the abortion counselling and treatment (in-clinic or self managed, self reported /estimated gestational length and contraceptive choice.

Incomplete abortion will be defined as products of conception remaining in the uterus with continued bleeding, bulky uterus, and open cervix at examination, possibly necessitating surgical evacuation at the discretion of the provider or at the woman's request derived from patient records.

Adverse events (AEs) will be recorded. The completeness of the abortion and any AEs will be identified by the on line follow up and by clinical examination.

Data management will be organized locally by data entry personnel and at the WHO centre, Karolinska. Data will be entered by use of a clinical trial software, checked for accuracy, and corrected after consultation of clinical records and research assistants, and reviewed monthly by the Study Coordinator at the WHO centre with further checking of clinic records as necessary.

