### Randomization procedure

Randomization: We will use a computer-generated randomization scheme with a varying block size. Randomization will be performed :1 by a midwife in the abortion clinic at the time of the first telephone consultation after the patient has been judged eligible for participation and has given her oral informed consent. Allocation to study group will be done after completion of a checklist of inclusion and exclusion criteria by opening consecutively numbered opaque, sealed, envelopes containing the randomisation group for each participant. Women will be identified through a patient log.

Women will be randomly assigned to either Group I) telemdicine counselling or Group II) standard face-to-face counselling. Women in group I will be given the address to a designated website and an appointment for ultrasound scan and pick up of medication while women in group II will be given an appointment to the abortion clinic. Medical abortion will be performed according to the Swedish national guidelines. Women will receive mifepristone (LinePharma, Paris, France) 200 mg orally at the clinic (counts as Day 1). Twenty-four to 48 hours later women self-administer 800 mcg misoprostol vaginally or sublingually (4 tabl Cytotec® 200 mcg, Pfizer, New York, USA). If bleeding has not started or is scant women will be advised to administer a second dose of 400mcg misoprostol sublingually 3 hours later. Follow-up will be done 2 weeks after treatment and outcome of abortion assessed primarily by low sensitivity urinary hCG test. The study will not be masked.

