### 8. Statistical analysis plan; power calculations - sample size

Sample size

The hypothesis to test is a non-inferiority hypothesis. The aim is to prove that telemedicine counseling is not inferior compared to standard abortion treatment. The expected efficacy rate (primary outcome) is 97.5% in both groups. The non-inferiority margin is set at 3%. The primary hypothesis will be tested by constructing a 95% confidence interval (CI) for the difference between the two treatments (intervention-control). If the upper limit of the CI is less than 3% the intervention will be declared as non-inferior to standard abortion care. In total 635 patients per group (1370 in total) is needed to obtain a power of 90%. To compensate for a 10% loss to FU an additional 138 women will be added to include 754 patients per group (total 1508 women).

Numbers and proportions of women having failed abortion and surgical intervention for incomplete abortion will be calculated by intervention. Both interventions will be compared using both absolute and relative measures with 95% confidence intervals. An intention-to-treat analysis as well as a per-protocol analysis will be performed. To evaluate the differences between the groups regarding independent nominal data such as side-effects and compliance, the chi squared test will be used. Continuous variables with a normal distribution, will be analysed using the Student's t-test whereas variable which are not normally distributed, such as age, GA (self-estimate vs LMP vs US) will presented as medians (range) and compared using Mann-Whitney U-test. Discrete numerical variables such as parity and bleeding days will be presented as means (range) and assessed for normality and comparison using the t-test or the Mann-Whitney U-test. Numeric variables (time lost from work and number of unplanned visits/consultations) will be analysed using analysis t-test. Results will be considered statistically

significant if P-value < 0.05. An independent data and safety monitoring committee will evaluate AE/SAE and make decisions if the trial should be stopped or continue as planned. Reason for stopping the trial could be a high failure rate or low acceptability rate in the intervention group. The plan for analysis and the study protocol has been developed in collaboration with prof. [name], Statisticon AB.

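### The plan gives an elective clinic follow-up visit to the control group and states none for telemedicine women, so part of the primary difference could come from the follow-up route

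*Combined protocol and SAP*

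**What the plan says.** **Follow-up meant to be common.** The end of the background (under Women-on-web) describes the trial population as "women who chose medical abortion up to 63 days of gestation with home administration of misoprostol and self assessment of the outcome". Section 2 (Participants) likewise recruits women who ask for home self-assessment. Section 3 (Interventions) states "Both groups: Self assessment of outcome will be done by the hCG CheckTop test", and adds an online questionnaire and a review of patient records after 30 days. Section 6 (Follow-up) gives both groups a telephone call or web questionnaire at about three weeks.

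**The difference.** The next sentence under Follow-up is "Women in the clinical routine group could choose to come back to the clinic for follow up". The clinical routine group is Group 2, the control. No section states a matching option for Group 1.

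**The outcome it touches.** Section 4 defines success as "complete abortion without ongoing intrauterine pregnancy or surgical intervention for incomplete abortion within 30 days of the abortion treatment". Incomplete abortion is described there as "products of conception remaining in the uterus with continued bleeding, bulky uterus, and open cervix at examination". The same definition leaves the decision to operate open to judgement and preference; its wording on this is "possibly necessitating surgical evacuation at the discretion of the provider or at the woman's request". Section 4 also says that completeness will be identified partly by clinical examination. Under Randomization procedure: "The study will not be masked".

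**The concern.** The randomised factor is counselling. For the difference in failures to be read as an effect of counselling, the two arms need the same chance of an examination that can lead to surgery. As written, a control woman may return to the clinic without a symptom or a positive test. For a telemedicine woman the plan describes contact in case of need.

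An examination can lead to discretionary surgery that would not otherwise have taken place by day 30, and such surgery may be recorded as a primary failure. If that adds control failures, the intervention-minus-control difference shrinks and non-inferiority is easier to declare. An examination can also reassure and avert surgery, which works the other way and costs power.

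The 30-day record review is the same in both arms, but it counts surgery already done and does not equalise the chance of having a visit. The intention-to-treat and per-protocol analyses in section 8 both keep the difference, and no other planned analysis addresses it.

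**Working it through.** **Inputs from section 8.** Expected efficacy is 97.5% in both groups, so failure is 2.5%. On the margin: "The non-inferiority margin is set at 3" per cent, taken here as percentage points. The test uses a 95% confidence interval, so the one-sided level is 0.025. Power is 90%, with 635 per group. Recruitment is 754 per group, allowing for 10% loss.

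**The plan's own figure.** Without continuity correction, n = (1.960 + 1.282)² × 2 × 0.975 × 0.025 / 0.03² = 569.2, so 570 per group. With the correction, n = (570/4) × [1 + √(1 + 4/(570 × 0.03))]² = 634.9, so 635. The per-group figure reproduces. (The printed total of 1370 is 2 × 685; that is a separate matter and is not used here.)

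**Number followed.** 754 × 0.9 = 678.6, about 679 per arm. Expected failures per arm: 0.025 × 679 ≈ 17.

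**Assumption.** The documents give neither the uptake of the visit nor its yield. Let b be the extra control failures: b = uptake × extra failures among those who attend. For example:
- 10% × 1 point = 0.1 points
- 10% × 2.5 points = 0.25 points
- 20% × 2.5 points = 0.5 points
- 40% × 2.5 points = 1.0 point

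A yield of 2.5 points doubles the plan's whole expected failure rate among attenders, so the larger values of b are demanding.

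**False non-inferiority when telemedicine is truly 3 points worse.** On the failure scale, pT = 0.055 and pC = 0.025 + b.

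SE = √{[pT(1 − pT) + pC(1 − pC)]/678.6}

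P(declare) = Φ{[0.03 − (pT − pC)]/SE − 1.96}

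At b = 0.5 points: SE = 0.01093, 0.005/0.01093 = 0.457, and Φ(0.457 − 1.96) = 6.6%.

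The last column is an exact binomial enumeration with n = 679, adding 1/n to the upper confidence limit.

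| b (points) | Extra control failures (women) | Normal approximation | Continuity-corrected, exact |
|---|---|---|---|
| 0 | 0 | 2.5% | 2.1% |
| 0.1 | 0.7 | 3.1% | 2.7% |
| 0.25 | 1.7 | 4.2% | 3.6% |
| 0.5 | 3.4 | 6.6% | 5.7% |
| 1.0 | 6.8 | 14.2% | 12.2% |

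**Opposite direction.** Suppose the arms are truly equal (pT = 0.025) and visits lower control failures by 0.5 points (pC = 0.020). Power falls from 94.3% to 87.4%, or from 91.8% to 82.7% with the continuity-corrected interval. At 20% uptake this would require attenders to have no failures at all (0.20 × 2.5 = 0.5), so it too is a large effect.

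**The case against.** The case on the other side has real force.

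- **Silence is not exclusion.** A reader might infer that telemedicine women are barred from a clinic visit. The documents do not say so. All women receive help-desk details and advice on when and where to make contact, and unscheduled visits are recorded. What is written is an elective visit for one group and nothing on the point for the other. This stands.
- **The definition narrows the route.** Incomplete abortion requires continued bleeding as well as examination findings. Silent retained tissue found at an elective visit does not qualify as written; surgery for it would fall under the secondary outcome of surgery for other indications. A woman who keeps bleeding has a symptom that can bring her to care in either arm. What remains is loose application of the definition and discretionary surgery. This stands.
- **Ongoing pregnancy is largely covered.** A reader might infer that ongoing pregnancies would be missed in the telemedicine arm. The shared hCG test, the questionnaire with reminders and the 30-day record review make that a minor part of the problem.
- **The visit may belong to standard care.** Section 8 compares telemedicine with standard abortion treatment, so a pragmatic reading would keep the visit in the comparison. This does not remove the point, because the stated question concerns counselling, with self-assessment in both arms.
- **Size and sign are assumed.** This is correct, and for that reason the table starts at zero and the opposite direction is shown.

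**Conclusion.** The point holds in a limited form. The written follow-up differs by arm, and the difference can reach the primary outcome through unmasked, discretionary surgery after an examination. Few failures are expected, about 17 per arm, so a handful of women matters.

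A reader might go further and conclude that the trial is biased towards non-inferiority. The documents do not support that: they give no uptake, no yield and no direction. If extra control failures arise, false non-inferiority at a true 3-point deficit runs from 3.1% at 0.1 points to 14.2% at 1.0 point, against 2.5% with none. If visits avert surgery, the cost is power. These figures rest on assumed values of b, 2.5% underlying failure in controls, about 679 followed per arm and the normal approximation. The continuity-corrected figures are somewhat lower.

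The plan should be changed, because the remedy is small. Confidence is medium: the difference is on the page, but its effect is unknown.

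**What to change.** - **One follow-up rule for both arms.** Home test plus questionnaire or call for everyone, with a clinic visit on the same terms in each arm: positive or invalid test, symptoms, or the woman's request. If routine care must keep the elective visit, offer it equally to telemedicine women.
- **Visit reason.** Record each visit within 30 days as elective or as prompted by test or symptoms, and report visits and resulting surgery by arm.
- **Apply the definition.** Count surgery as a primary failure for incomplete abortion only when the section 4 definition of incomplete abortion is met.
- **Women already followed under the unequal rule.** An analysis that drops surgery arising only from elective visits may be added, but it should be labelled a one-sided bound. If elective visits took place only among controls, it removes failures from that arm alone, including women who would have presented later anyway, and so may under-count control failures.

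**Cost.** A changed protocol sentence, one data field and one table. The database already holds unscheduled visits, and the 30-day record review may supply past visit reasons. The downside is a few more clinic visits in the telemedicine arm and some judgement in coding reasons.

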### Randomization procedure

Randomization: We will use a computer-generated randomization scheme with a varying block size. Randomization will be performed :1 by a midwife in the abortion clinic at the time of the first telephone consultation after the patient has been judged eligible for participation and has given her oral informed consent. Allocation to study group will be done after completion of a checklist of inclusion and exclusion criteria by opening consecutively numbered opaque, sealed, envelopes containing the randomisation group for each participant. Women will be identified through a patient log.

Women will be randomly assigned to either Group I) telemdicine counselling or Group II) standard face-to-face counselling. Women in group I will be given the address to a designated website and an appointment for ultrasound scan and pick up of medication while women in group II will be given an appointment to the abortion clinic. Medical abortion will be performed according to the Swedish national guidelines. Women will receive mifepristone (LinePharma, Paris, France) 200 mg orally at the clinic (counts as Day 1). Twenty-four to 48 hours later women self-administer 800 mcg misoprostol vaginally or sublingually (4 tabl Cytotec® 200 mcg, Pfizer, New York, USA). If bleeding has not started or is scant women will be advised to administer a second dose of 400mcg misoprostol sublingually 3 hours later. Follow-up will be done 2 weeks after treatment and outcome of abortion assessed primarily by low sensitivity urinary hCG test. The study will not be masked.

### Discontinuation

After recruitment, women may withdraw from the trial at any time if they do not wish to participate. This will not affect future treatment, which will then be according to clinical standard.

